8.4 Early Discontinuation of Therapy

- 8.4.1 Participants discontinuing therapy early (i.e., PD or stable disease, administrative reasons, participant non-compliance, etc.) will have a medical history update and complete physical examination. The examination will include performance status and blood drawn for the following studies within 1 month after treatment discontinuation, unless otherwise noted. See Section 4.7 for a list of reasons for study termination. Participants will be followed for survival only for 5 years after the last date of treatment:
 - 8.4.1.1 CBC with differential.
 - 8.4.1.2 Serum chemistries: electrolytes (Na, K, Cl, bicarbonate, Ca, Mg, and phosphorus), glucose, blood urea nitrogen (BUN), creatinine, total bilirubin, alkaline phosphatase (ALP), LDH, total protein, albumin, AST and ALT.
 - 8.4.1.3 CD4 and CD8 cell count (do not repeat if done within 1 month from removal from treatment).
 - 8.4.1.4 HIV-1 RNA viral load to be assessed by any FDA-approved viral load assay (evaluated at the local laboratory, do not repeat if done within 1 month from removal from treatment).
 - 8.4.1.5 Pharmacokinetic/Immunogenicity studies in select Phase II participants only. See Section 10.1 and Appendix IX for time points and sample processing.
 - 8.4.1.6 Blood samples will be taken for analysis of latent and HIV reservoirs. See Section 10.0 and Appendix XII for time points needed, sample processing, and shipping instructions (do not repeat if done within 1 month from removal from treatment).
 - 8.4.1.7 Plasma samples to be taken for EBV tumor DNA studies. See Appendix XI for sample processing and shipping instructions. This will only be performed on the Phase II portion of the study.
 - 8.4.1.8 Plasma samples to be taken for and cytokine studies. See Appendix XI for sample processing and shipping instructions. This will only be performed on the Phase II portion of the study.

9.0 EFFICACY AND SAFETY MEASUREMENTS

9.1 Efficacy Measurements

All participants will be evaluated for clinical response by physical examination prior to receiving treatment on each cycle. The exam should occur within 3 days prior to the start of each cycle, but may occur on Day 1 of cycle.

All participants will be evaluated for clinical response by imaging studies after by FDG-PET/CT at the completion of cycle 2 and at the completion of therapy (See Section 5.0).

9.2 Response Assessment

Response is currently assessed on the basis of clinical, radiologic, and pathologic (i.e., bone marrow) criteria.

Definition of Response:

The response definitions used for this study are the 2007 Cheson criteria. A major distinction in the 2007 criteria is that PET/Gallium studies are used to facilitate the distinction between persistent tumor and scar/fibrosis.

Complete Response (CR):

- 1. Complete disappearance of all detectable clinical evidence of disease and diseaserelated symptoms if present before therapy.
- 2a. Typically FDG-avid lymphoma: In participants with no pretreatment PET scan or when the PET scan was positive before therapy, a post-treatment residual mass of any size is permitted as long as it is PET negative.
- 2b. Variably FDG-avid lymphomas/FDG avidity unknown: In participants without a pretreatment PET scan, or if a pretreatment PET scan was negative, all lymph nodes and nodal masses must have regressed on CT to normal size (1.5 cm in their greatest transverse diameter for nodes > 1.5 cm before therapy). Previously involved nodes that were 1.1 to 1.5 cm in their long axis and more than 1.0 cm in their short axis before treatment must have decreased to 1.0 cm in their short axis after treatment.
- 3. The spleen and/or liver, if considered enlarged before therapy on the basis of a physical examination or CT scan, should not be palpable on physical examination and should be considered normal size by imaging studies, and nodules related to lymphoma should disappear. However, determination of splenic involvement is not always reliable because a spleen considered normal in size may still contain lymphoma, whereas an enlarged spleen may reflect variations in anatomy, blood volume, the use of hematopoietic growth factors, or causes other than lymphoma.
- 4. If the bone marrow was involved by lymphoma before treatment, the infiltrate must have cleared on repeat bone marrow biopsy. The biopsy sample on which this determination is made must be adequate (with a goal of > 20 mm unilateral core). If the sample is indeterminate by morphology, it should be negative by immunohistochemistry.

Partial Response (PR) Requires all of the Following:

1. At least a 50% decrease in sum of the product of the diameters (SPD) of up to six of the largest dominant nodes or nodal masses. These nodes or masses should be selected according to all of the following: they should be clearly measurable in at

least two perpendicular dimensions; if possible they should be from disparate regions of the body; and they should include mediastinal and retroperitoneal areas of disease whenever these sites are involved.

- 2. No increase should be observed in the size of other nodes, liver, or spleen.
- 3. Splenic and hepatic nodules must regress by 50% in their SPD or, for single nodules, in the greatest transverse diameter.
- 4. With the exception of splenic and hepatic nodules, involvement of other organs is usually assessable and no measurable disease should be present.
- 5. Participants who achieve a CR by the above criteria, but who have persistent morphologic bone marrow involvement will be considered partial responders. When the bone marrow was involved before therapy and a clinical CR was achieved, but with no bone marrow assessment after treatment, participants should be considered partial responders.
- 6. No new sites of disease should be observed.
- 7. Typically FDG-avid lymphoma: for a participant with no pretreatment PET scan or if the PET scan was positive before therapy, the post-treatment PET should be positive in at least one previously involved site.
- 8. Variably FDG-avid lymphomas/FDG-avidity unknown: if a pretreatment PET scan was negative, CT criteria should be used.

Stable Disease (SD) is Defined as the Following:

- 1. A participant is considered to have SD when he or she fails to attain the criteria needed for a CR or PR, but does not fulfill those for progressive disease (see Relapsed Disease [after CR]/Progressive Disease [after PR, SD]) below.
- 2. Typically FGD-avid lymphomas: the PET should be positive at prior sites of disease with no new areas of involvement on the post- treatment CT or PET.
- 3. Variably FDG-avid lymphomas/FDG-avidity unknown: if the pretreatment PET was negative, there must be no change in the size of the previous lesions on the post-treatment CT scan.

Relapsed Disease (after CR)/Progressive Disease (after PR, SD):

- 1. Lymph nodes should be considered abnormal if the long axis is more than 1.5 cm regardless of the short axis. If a lymph node has a long axis of 1.1 to 1.5 cm, it should only be considered abnormal if its short axis is more than 1.0. Lymph nodes 1.0 x 1.0 cm will not be considered as abnormal for relapse or progressive disease.
- 2. Appearance of any new lesion more than 1.5 cm in any axis during or at the end of therapy, even if other lesions are decreasing in size. Increased FDG uptake in a previously unaffected site should only be considered relapsed or progressive disease after confirmation with other modalities. In participants with no prior history of pulmonary lymphoma, new lung nodules identified by CT are mostly benign. Thus, a therapeutic decision should not be made solely on the basis of the PET without histologic confirmation.
- 3. At least a 50% increase from nadir in the SPD of any previously involved nodes, or in a single involved node, or the size of other lesions (e.g., splenic or hepatic nodules). To be considered progressive disease, a lymph node with a diameter of the short axis of less than 1.0 cm must increase by 50% and to a size of 1.5 x 1.5 cm or more than 1.5 cm in the long axis. At least a 50% increase in the long est.

diameter of any single previously identified node more than 1 cm in its short axis. Lesions should be PET positive if observed in a typical FDG-avid lymphoma or the lesion was PET positive before therapy unless the lesion is too small to be detected with current PET systems (< 1.5 cm in its long axis by CT).

Recurrent Disease is defined as the appearance of tumor following documentation of a complete remission.

*Time to Response* is defined as time from the first dose of chemotherapy until documentation of first response.

*Time to Progression* is defined as time from initiation of chemotherapy to documentation of first progression.

Response Duration is defined as the time from first documentation of response to documentation of first progression.

Safety Measures

All AE will be monitored by ongoing review of reported adverse events by the protocol chair and the AMC Operations and Data Management Center, and will be discussed during the monthly investigators' Lymphoma Working Group conference calls (see Section 4.7 for rules for early study termination).

10.0 CORRELATIVE STUDIES

For this protocol, we propose three correlative studies: miRNA analysis (see Section 10.2 and Appendix VIII), Tissue Microarray Studies (TMA) (see Appendix VIII), and Pharmacokinetic studies (PK) (see Section 10.1 and Appendix IX). We will collect either the paraffin blocks or Cores from these tissue and multiple unstained slides as a requirement for study entry to perform the miRNA and the TMA studies in addition to central pathology diagnosis confirmation. We will then correlate findings with the outcomes of participants enrolled on this trial in addition to their HIV infection characteristics. Please see Section 10.1 and Appendix IX for a detailed description of the PK studies to be performed in this clinical trial using serum isolated from participants during therapy.

In addition, upon acquisition of funding, we propose 3 more correlative studies. 1) We will analyze the Granzyme B to FoxP3 ratio on paraffin sections, to determine if these values, which have been reported to be prognostic indicators in non-HIV associated cHL, also correlate with outcome in HIV-HL⁶² (see Appendix VIII). 2) We will also screen participant's plasma for molecules associated with immune activation and inflammation. specifically sCD30, CXCL13, IL-6 and IL-10. In a prior study in the AMC, we also assessed the effect of treatment for AIDS-associated NHL on plasma levels of these biomarkers, finding that treatment resulted in a marked decrease in many of these molecules, and that pre-treatment initiation plasma levels of CXCL13, IL-6 and IL-10 were predictive of subsequent CR to treatment^{63,64}. In fact, in multivariate analysis, CXCL13 levels proved to be better predictors of subsequent clinical response that IPI or other established prognostic markers^{63,64}. We will confirm if these molecules are prognostic in HIV-HL as well as these molecules were also found to be elevated in these participants^{65,66} (see Appendix X). 3) As HIV-HL is co-infected with EBV, an attempt will be made to detect levels EBV derived tumor DNA in the plasma and use this as a tumor marker and a prognostic one. To do these last two studies, we will also collect plasma samples over time throughout therapy and post therapy to see how these biomarkers change over time (see Appendix XI).

10.1 Pharmacokinetic/Immunogenicity Studies

Chemotherapy-HAART interactions have become more pronounced in the transition from single agent HIV therapies to the era of cART as protease inhibitors (PI) and non-nucleoside reverse transcriptase inhibitors (NNRT) are potent inhibitors (i.e., ritonavir) or inducers (i.e., efavirenz) of the cytochrome P450 system, in particular CYP3A4. As described in Section 7.1.4, brentuximab vedotin is an ADC whose conjugate MMAE is also metabolized via CYP3A4. As pharmacokinetic interactions between HAART and brentuximab vedotin are unknown, these interactions will be carefully monitored. Drug levels will be determined by assaying brentuximab vedotin, total antibody, and the free drug MMAE concentration over time. The formation of anti-brentuximab vedotin antibodies will be also assessed at the time points summarized below in Appendix IX. As the use of most potent inhibitor of CYP3A4 (i.e., ritonavir) is prohibited in this study, the pharmacokinetic data will compare two patient populations, those taking chemotherapy with concurrent efavirenz and non-efavirenz-based HAART. The pharmacokinetic data of 6 participants from each group will be assessed in the phase II portion of the clinical trial, once the maximum tolerated dose has been determined. Please see Appendix IX for a
detailed description of sample processing, time points that need to be assayed, shipping, and the assays involved.

10.2 Micro RNA Analysis of HIV-Associated Hodgkin Lymphoma

Mature microRNAs (miRNAs) are small non-coding RNAs that act as negative regulators of protein synthesis by covalently binding to the single stranded mRNA⁶⁷⁻⁷¹. Once bound, the RNA-induced silencing complex (RISC) is formed⁶⁷⁻⁷¹. Over 800 miRNAs have been identified in humans. These miRNAs play important roles in every cell function including cell proliferation/differentiation and can act as tumor suppressor and/or oncogenes^{72,73}. Viruses also encode miRNA, and interactions between viral and host miRNAs affect host protein expression in specific manners to either promote viral replication or, in certain instances, cellular transformation 1-4. The most common viruses identified to play a role in HIV-associated cancer tumorigenesis, HHV-8, HPV, and EBV together express over 40 miRNAs^{67,68}. Viral miRNAs transform cells by various mechanisms. MiR-BHRF1-1 and miR-BART1, EBV expressed miRNAs, inhibit the tumor suppressor p53 and activate BCL-2 (an anti-apoptotic protein), respectively^{67,68}. These miRNA combinations found in profile analysis are so specific that they define specific cancers as precisely as mRNA gene profiling⁷⁴. Since many of the targets of the miRNAs are known, clues into the mechanisms of transformation and potential targets for therapy can be obtained⁶⁷⁻⁷⁰. Unfortunately, little data exist on the miRNA profiles on HIV-associated lymphoma, and no data exist on HIV-HL. It is known that hRS cell, can be co-infected in non-HIV participants, hRS cells are co-infected in 30-40% of the cases^{15,17,18}. In HIV-HL the infection rate of the hRS cells with EBV range from $80-100^{\%15,17,18}$. The molecular basis of transformation is unclear. In HIV-HL, the lymphocytic depleted histologic subtype of HL is more common than the non-HIV or the non-HIV EBV-associated HL. HIV-HL also is the most aggressive form of HL, imparting the worst prognosis. MiRNA profiling of HL in non-HIV-infected population identified unique molecular signatures so specific that just looking at the miRNA profile, a 100% correlation was made as to which tumors were infected with EBV⁷⁵. Which types of EBV miRNA are expressed in HIV-HL vs. non-HIV HL and whether HIV effects the expression of different miRNAs in HL have never been assessed. Because the clinical course and histology differ from classic HL and EBV-associated HL in non-HIV infected individuals, we speculate that HIV-associated Hodgkin Lymphoma has a different molecular signature.

To this end, as a correlative study in this clinical trial, we will analyze the miRNA profiles of the paraffin-embedded tumor samples of the study participants. This analysis will be performed using high throughput sequencing to comprehensively define the miRNA expression, as described previously. As controls, reactive lymph nodes from HIV-infected and uninfected participants, as well as non-HIV HL samples that are EBV positive will be used.

We will also correlate miRNA expression with overall survival, tumor response to therapy, histologic subtype of HIV-HL, and HIV disease characteristics to identify miRNAs that could act as prognostic and diagnostic markers.

Please see Appendix VIII for a detailed description of specimens required, sample processing, and shipping.

10.3 Effects of AVD-Brentuximab Vedotin on T-cell Subsets in vivo

Brentuximab vedotin has the potential to destroy all cells that are CD30 positive as seen in the HRS cell. Heiser *et al.* investigated the distribution of CD30 expression across all T-cell subsets and demonstrated CD30 expression was identified mostly in the T-regulatory cells.⁹³ While these cells have many roles, one of their main functions is to suppress CD8 and CD4+ T-cell proliferation. When CD8+ and FOX-P3+ T-Regulatory cells were co-incubated in vitro, brentuximab vedotin challenge resulted in a decrease in T-regulatory T-cell number, and an increase in CD8+ T-cells number.⁹³ Preliminary data from AMC-085 identified that CD4+ T-cells as well as CD8+ T-cells increased about 1 month after AVD-BV treatment in nearly all subjects enrolled to date (unpublished data).

To see if this was a brentuximab vedotin effect, we compared data with 54 patients with HIV-associated Hodgkin Lymphoma treated with ABVD alone at County Hospital in Chicago (unpublished data). To exclude the possibility that uncontrolled HIV was a cause for a drop in the CD4+ T-cell counts in these subjects, patients with undetectable viral loads were identified. In this ABVD comparison group, 80% of the subjects had drops in CD4+ T-cell counts about 1-2 months post chemotherapy, the opposite of the effect seen in AMC 085. Additionally, when CD8+ T-cell counts were analyzed in subjects treated with ABVD, 100% had drops in CD8+ T-cell counts.

The fact that patients with **ABVD** had drops in CD8 and CD4+ T-cell counts while trial participants receiving **AVD**-BV had elevations suggests brentuximab vedotin is the causative agent of the elevation, possibly due to T-regulatory T-cell destruction. The hypothesis of this correlative study is that brentuximab vedotin achieves T-regulatory T-cells destruction causing CD8 and CD4+ T-cell count elevation The purpose of this correlative study is to evaluate whether this is the mechanism seen *in vivo* in participants with HIV-associated cHL.

To prove this mechanism, we will use cytokine analysis via multiplex, flow cytometry and CyTOF (cytometry by time of flight) to confirm which cytokines and T-cell subsets are altered over time. Cytokine analyses will be performed on all participants enrolled at [name] laboratory (AMC Core Biomarkers Laboratory), on existing samples for cytokine analysis. The T-cell subset and cytokine assays performed by CyTOF and flow cytometry will be performed by [name] laboratory (Ohio State University AMC site) for up to 10 participants. The cells required will be aliquots from blood samples already collected from participants in the optional HIV viral reservoir studies in Appendix XII, who have also consented for the additional use of his/her specimens in future research by the ACSR. Please see Appendix XIV for a detailed description of sample processing, time points that need to be assayed, shipping, and the assays involved.

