- 3.1.16 Participants are required to be on antiretroviral regimens that are in accordance with the current International AIDS Society guidelines concurrently with chemotherapy. The specific agents are at the discretion of the Investigator and the use of investigational agents currently available on an expanded access basis is allowed. Use of experimental antiretroviral agents or those containing zidovudine (including Combivir and Trizivir) or ritonavir (includes Norvir[®] or Kaletra[®]), Cobicistat, Didanosine (Videx[®] or Videx EC[®]), or similar potent CYP3 inhibitors are

prohibited, as explained in Section 2.4.5. In order to be eligible, participants taking zidovudine or ritonavir, Cobicistat, Didanosine, or other CYP3 inhibitors must change to a different regimen 7 days prior to therapy initiation. Changes to HAART therapy during the study may be made if medically necessary (toxicity, failure of regimen, etc.). Participants must be on HAART for at least 7 days prior to therapy.

- 3.1.17 Negative for Hepatitis B, or if infected with Hepatitis B, receiving anti-Hepatitis B therapy. All participants will be required to be screened for Hepatitis B. Per IDSA and AASD guidelines, those participants that show no immunity, defined by the lack of Hepatitis B surface antibody, and show evidence of chronic infection (i.e., HBsAg+, HBcore+, HBsAB-) will be required to be on anti-Hepatitis B therapy during the study in order to be eligible. Patients will be permitted to enroll in the study provided normal liver function tests (see Section 3.1.9) and no evidence of cirrhosis. The exact Hepatitis B therapy will be at the discretion of the infection disease specialist or investigator. However, all patients who present with acute hepatitis B or show normal transaminases and are HBsAg+ and IgM+ for Hepatitis core antigen will not be eligible for trial enrollment.
- 3.1.18 Patients diagnosed with Hepatitis C who are Hepatitis C antibody positive, whether Hepatitis C RNA level is measurable or not, must have no evidence of cirrhosis and have liver function tests that conform to Section 3.1.9.
- 3.1.19 Brentuximab vedotin is partially metabolized via the CYP3A4 pathway and is cleared from the cells via the P-glycoprotein pump. Therefore, participants must discontinue use of the following agents within 7 days prior to therapy as per Appendix XIII.
 - Strong CYP 3A4 inhibitors that treat HIV, see 3.1.16.
 - Other strong CYP3A inhibitors.

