8.1 Screening/Baseline Evaluations

Unless otherwise specified, the following evaluations must be performed within 6 weeks prior to participant registration:

- 8.1.1 AIDS and Cancer Specimen Resource (ACSR) Consent for optional donation. It is required that AMC sites present the ACSR donation option to participants. (See Appendix VI for ACSR Informed Consent Form and Appendix V for ACSR Specimen Preparation and Shipping Instructions).
- 8.1.2 Medical history, history of drug allergies, history of current and past anti-retroviral regimens, if available; and history of any prior AIDS-defining conditions. Date of initial lymphoma diagnosis is required, with a copy of the pathology report in the medical record. Presence of systemic "B" symptoms should be noted, as well as other symptoms of cHL. Current concomitant medication list, including all anti-retroviral, anti-viral, antibiotics, and opportunistic prophylaxis should be obtained.
- 8.1.3 Physical examination, including performance status (see Appendix III Performance Status Scale), vital signs (weight, height, body surface area), neurological examination, and if possible, two dimensional measurement of all palpable, peripheral lymph nodes and measurement of other sites of disease present on physical exam.
- 8.1.4 A combined FDG-PET/CT or FDG-PET + CT scan with and without IV contrast is required for this study. If a participant has an allergy to IV contrast, a non-IV contrast CT scan will be permitted. To ensure consistency between all centers, FDG-PET/CT scans at diagnosis should be conducted no more than 28 days before enrollment.

If the CT scan of a PET/CT hybrid is performed with both oral and IV contrast with contrast enhancement in the arterial and/or portal venous phase, with at least a 2-slice CT, and is acquired with at least 80 mAs and CT scans are obtained with contiguous sections (with a maximum of 5 mm slice thickness), then the pre-treatment PET/CT scan alone will suffice for participants enrolled on this trial. If no contrast is used in the FDG-PET/CT, an additional CT scan with contrast is required of the neck, chest, abdomen, and pelvis, see 8.1.5 below.

- 8.1.5 CT scan of the neck (if palpable lymphadenopathy only), chest, abdomen and pelvis with and without IV contrast will be required. If the CT portions of the FDG-PET/CT combination scan is a non-contrast CT scan, then a separate CT scan with and without IV contrast will be required.

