11.4 Analysis of Secondary Endpoints

Descriptive summaries and exploratory analyses for secondary objectives will be conducted. Significance for comparisons will be at the p<0.05 level.

Secondary objectives include:

1. To evaluate toxicity of AVD and brentuximab vedotin with HAART.

- 2. To estimate the partial response rate, complete response rate, overall survival (OS), event free survival at 2 and 5 years. To evaluate effect of AVD and brentuximab vedotin on CD4 and CD8 counts after 2 cycles, 6 cycles, and every 3 months after treatment completion for one year.
- 3. To evaluate effect of AVD and brentuximab vedotin on viral load after 2 cycles, 6 cycles, and every 3 months after treatment completion for one year
- 4. To investigate the prognostic value of FDG-PET scans at baseline and after 2 cycles in participant with HIV and HL with respect to 2 year progression free survival.
- 5. To evaluate HAART status at baseline for difference in outcome.
- 6. The characterization of histologic subtypes in HIV-HL in the HAART era.
- 7. To assess additional neurotoxicity in combination with HAART and AVD and brentuximab vedotin.

The frequency of AEs and their severity will be tabulated to evaluate tolerance of AVD and brentuximab vedotin with HAART. Further, binomial probabilities and their 95% confidence intervals will be used to estimate the response rates (i.e., partial response rate, complete response rate, overall response rate) and event free survival at 2 and 5 years of AVD and brentuximab vedotin for a treatment of participants with stage III/IV HIV-associated Hodgkin Lymphoma.

Repeated measures analysis of variance (ANOVA) models will be used to evaluate the effect of AVD and brentuximab vedotin on CD4 counts, CD8 counts and viral load after 1, 4, and 6 cycles, and every 3 months after treatment completion for one year.

Log-rank analysis will be used to investigate the prognostic value of FDG-PET scans at baseline, after 2 cycles and post-therapy in participants with HIV and HL with respect to progression free survival.

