2.0 BACKGROUND

Brentuximab vedotin has the potential to destroy all cells that are CD30 positive, as seen in the HRS cell. Heiser et al. attempted to understand the distribution of CD30 expression across all T-cell subets.⁹³ There data demonstrated that CD30 expression was identified mostly in the T-regulatory cells. While these cells have many roles, one of their main functions is to suppress CD8+ and CD4+ T-cell proliferation. In co-incubation experiments in vitro, it was demonstrated that when CD8+ and FOX-P3+ T-regulatory cells were co-incubated, as T-regulatory T-cells decreased in number CD8+ T-cells also increased in number when challenged with brentuximab vedotin.⁹³

Preliminary data from this study realized in an interim analysis identified that CD4+ Tcells as well as CD8+ T-cells increased in just about 1 month after AVD-BV treatment in essentially all subjects enrolled to date (unpublished data). To see if this was an effect of brentuximab vedotin, 54 patients with HIV-associated Hodgkin Lymphoma were identified at County Hospital in Chicago. To exclude the possibility that uncontrolled HIV was a cause for a drop in the CD4+ T-cell counts in subjects, patients with undetectable viral loads were identified. Of the patients with undetectable viral loads treated with ABVD, 80% of the subjects had drops in CD4+ T-cell counts about 1-2 months post chemotherapy. Additionally, when CD8+ T-cell counts (unpublished data). Based on the interim analysis of AMC-085, the increase in CD4 T cell counts was observed only in patients that were treated with AVD-BV but not with ABVD.

The fact the in subjects with ABVD had drops in CD8 and CD4+ T-cell counts while subjects with AVD-BV had elevations, points to brentuximab vedotin as the causative agent of the elevation. Combining this data with the data presented by Heiser and colleagues, points to the cause of the elevation as T-regulatory T-cell destruction. We hypothesize that brentuximab vedotin achieved T-regulatory T-cells destruction, thereby causing total CD8+ and total CD4+ T-cell count elevation. The purpose of this correlative study is to prove that this is the mechanism seen in vivo in subjects with HIV-associated cHL.

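### The CD4/CD8 model has no term for viral suppression or HAART timing, so in participants entered under AMC criteria CD4 recovery on new HAART can be read as an AVD-BV effect

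*Combined protocol and SAP*

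**What the plan says.** **Planned analysis.** AMC protocol Section 11.4 states: "Repeated measures analysis of variance (ANOVA) models will be used to evaluate the effect of AVD and brentuximab vedotin on CD4 counts". The sentence goes on to CD8 counts and viral load. French protocol Section 16.4 repeats it, and French Section 16.0 says that the AMC statistical center analyses French and US data together. Neither section names a covariate or a subgroup for this model.

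**Entry and baseline.** AMC Section 3.1.16 requires: "Participants must be on HAART for at least 7 days prior to therapy". Section 3.1 sets no upper limit on viral load. Section 8.1 says that, unless specified otherwise, "the following evaluations must be performed within 6 weeks prior to participant registration". Item 8.1.12.3 (CD4 and CD8) gives no shorter window, whereas the CBC must be within 2 weeks of registration and the viral load within 21 days of Cycle 1 Day 1 (C1D1). French Section 8.1, item 15, requires a viral load below 50 copies/mL.

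**Interpretation.** AMC Section 10.3 reports that CD4 and CD8 counts rose about a month after AVD-BV in nearly every participant so far. It compares them with 54 ABVD patients at one hospital, from whom "patients with undetectable viral loads were identified". The stated reason was to rule out uncontrolled HIV as the cause of CD4 falls in that group. There, "80% of the subjects had drops in CD4+ T-cell counts about 1-2 months post chemotherapy"; for CD8, "100% had drops in CD8+ T-cell counts". Section 10.3 concludes that the contrast "suggests brentuximab vedotin is the causative agent of the elevation, possibly due to T-regulatory T-cell destruction". Appendix XIV, Section 2.0, says that it "points to brentuximab vedotin as the causative agent of the elevation".

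**The concern.** A rise from baseline in a single-arm trial is attributed to treatment only if nothing else that raises the count changes over the same interval. Under AMC criteria something else can change: HAART may be new, and the baseline count may have been taken before it began. The planned model would put any resulting CD4 recovery into the time effect and report it as the effect of AVD-BV.

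The external contrast does not settle the matter, because the viral-load filter was applied to one side only. The ABVD patients were virally suppressed; no such restriction is stated for the trial participants. The plan thus treats HIV control as relevant to CD4 counts but removes it from one group.

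What is at stake is the reading of secondary objective 1.2.3 and the premise of the T-cell work in Section 10.3 and Appendix XIV. The primary endpoint (2-year PFS), the stopping rules and dosing do not depend on it.

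**Working it through.** The plan gives no figure for this point, so there is none to reproduce. Two checks are possible.

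**1. Can the baseline predate HAART?**

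Inputs, from the AMC protocol:
- screening window for CD4/CD8: 6 weeks = 42 days before registration (8.1, 8.1.12.3);
- registration to first dose: up to 7 days (3.5);
- minimum HAART before therapy: 7 days (3.1.16);
- first on-treatment count: Cycle 2 Day 1 (C2D1), 28 days after C1D1 (8.2.7).

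Results:
- baseline to C1D1, longest: 42 + 7 = 49 days;
- baseline to C2D1, longest: 49 + 28 = 77 days;
- baseline ahead of a HAART start 7 days before C1D1, longest: 49 − 7 = 42 days;
- HAART exposure at C2D1, shortest: 7 + 28 = 35 days.

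Section 3.5 encourages enrollment on the day of treatment or the day before. Even with same-day enrollment the baseline can be 42 days before C1D1, which is 42 − 7 = 35 days ahead of such a HAART start. So all of a new starter's HAART exposure can fall between baseline and the first on-treatment count.

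The documents also expect some viremic participants. Section 8.2.8 has a rule specific to those undetectable at baseline, and Appendix XII limits its baseline samples to that group. Section 2.3 reports an immunological response in 56% of patients in the cited study of ABVD with HAART.

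**2. How much of the contrast could new HAART produce with no brentuximab vedotin effect?**

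This is a ceiling, not an estimate. Let f be the share already suppressed at entry. Assume that they follow the ABVD pattern (80% fall, so 20% rise) and that every other participant's CD4 count rises on new HAART.

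Share with a CD4 rise = (1 − f) + 0.20 × f

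| f | Calculation | CD4 rises, at most |
|---|---|---|
| 0 | 1 + 0 | 100% |
| 10/51 = 0.196 | 0.804 + 0.039 | 84% |
| 20/51 = 0.392 (planned French share) | 0.608 + 0.078 | 69% |

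The ABVD reference is 20%. The true f among those enrolled so far is not given, and suppressed AMC-criteria participants would raise it. If half of all participants were new starters, the ceiling would be 0.5 + 0.5 × 0.20 = 60%. The formula is not applied to CD8, because no section shows that new HAART raises CD8.

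**The case against.** The strongest reply is that Section 10.3 gives a rationale, not an analysis. It is worded as a suggestion, followed by a hypothesis to be evaluated. Neither Section 11.4 nor Appendix XIV, Section 5.0, plans a test against ABVD, and Section 11.4 calls the secondary analyses descriptive and exploratory. That stands, and it limits the consequence. It does not answer the point about the ANOVA, which is planned and is meant to evaluate the effect of the regimen. Section 10.3 and Appendix XIV also go on to speak of proving the mechanism.

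Four stronger readings are tempting, and the documents do not support them.

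- *HAART explains the whole rise.* French entry requires fewer than 50 copies/mL, for 20 of 51 planned participants, which makes new HAART an unlikely explanation there. At that mix the ceiling is 69%, short of a rise in nearly everyone. The actual mix is not reported.
- *The T-cell mechanism work is confounded in the same way.* The CyTOF cells come from the reservoir samples. Their baseline draws are limited to participants with undetectable HIV-1 RNA and are taken about one week before C1D1 and again within 24 hours of it (Appendix XII, Section 3.0). That work covers at most 10 participants and does not require an unchanged regimen, so it does not repair the count comparison, but it already has the suppression filter.
- *CD8 is biased too.* No section shows a CD8 rise on new HAART, and the ABVD sentence on CD8 in Section 10.3 does not restate the viral-load restriction.
- *The bias can be stated in cells/µL.* The mean shift is the share of new starters times the HAART-only gain, and the documents give neither. Assuming 10–60% starters and a gain of 50–100 cells/µL gives 0.1 × 50 = 5 to 0.6 × 100 = 60, a twelvefold range with no source behind it.

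**Conclusion.** The concern holds for CD4 in participants entered under AMC criteria. They may be viremic and 7 days into HAART, their baseline can be up to 49 days before C1D1, and the pooled model has no term that would separate HAART recovery from an AVD-BV effect. The ABVD comparison is unmatched, because only that side was limited to undetectable viral load.

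The size is unknown, because the number of recent HAART starters is not reported. The ceilings of 69% to 100% CD4 risers show only that the contrast with 20% could be inflated. They rest on the assumption that every unsuppressed participant's count rises, which the documents do not show. For CD8 the possibility is open but not established. This is a moderate weakness in a secondary objective, worth correcting because the correction is cheap.

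**What to change.** In AMC Section 11.4 and French Section 16.4:
- add baseline viral suppression (undetectable or detectable) as a factor in the CD4/CD8 model, and state the threshold, since AMC item 8.1.12.4 accepts any assay that detects viremia above 200 copies/mL while French entry uses 50;
- where dates are available, add whether HAART was started before or after the baseline count;
- report the change separately in participants with undetectable baseline viral load who started HAART before the baseline count.

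In Section 10.3 and Appendix XIV, base any comparison with the virally suppressed ABVD group on that same subset.

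The data are largely in hand: baseline viral load (8.1.12.4), antiretroviral history (8.1.2) and the antiretroviral records (7.3.6). The changes can therefore be applied to participants already enrolled.

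Costs: the subset is smaller and its intervals wider. HAART start dates may be incomplete, because the history is collected only where available and Section 7.3.6 specifies start and stop dates only for regimen changes. All French participants should fall in the undetectable group, so the suppression factor will also carry part of any country difference. A repeat count at C1D1 would be an extra test and could not help those already enrolled, so the fix does not rely on one. Treatment rules and the primary endpoint are unchanged.
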